6.3.2. KCELABGP_LAB

The laboratory tests are coded with two possible coding systems: Medidoc[5] or LOINC codes.[6] All Medidoc codes will be mapped to their corresponding LOINC codes so that the entire database was available in one universal code set. The recoding will be performed semi-automatically. Where possible the ReTaM database of laboratory codes will be used as a mapping table.[7] However, many codes will need to be mapped manually. For this manual mapping two sources will be used: the LOINC reference website (<https://search.loinc.org>) from the Regenstrief Institute and the latest release of Medidoc codes available from Corilus. For a small set of laboratory tests, the meaning of the original Medidoc code is not retrievable and these tests will not be recoded. Observations that are not laboratory test results will be deleted. This includes observations such as weight, height, body mass index, lipemic index, hemolytic index, and insignificant text information.

If reference values (upper limit and lower limit) of the laboratory result value are missing, these will be imputed. If possible, the reference values provided by the laboratory will be used. Sometimes the reference values for the same test differ across laboratories. If reference values are dependent on sex and or age, these variables are considered. Some reference values are dependent on additional clinical information which is not available. For example, the reference value for HbA1c is dependent on whether the test is ordered as a screening test or for the follow-up of a treated diabetes. This

information is not readily available and a reference value that takes both indications into account will be used.

Alphanumeric laboratory results will be recoded to either 'TRUE' (for a normal result), 'FALSE' (for an abnormal result) or 'MISSING' (if the result implies that the test could not be performed). This recoding is done based on the interpretation of the result in relation to the test type. Alphanumeric and numeric results will then be divided into different columns and based on the reference values, the laboratory result will be calculated as 'TRUE' (normal result within the reference value range) or 'FALSE' (abnormal result outside of the reference value range).

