10.1. Outcome definitions

10.1.1. Primary outcome appropriateness

We chose to use a restrictive definition to appropriateness as defined by Zhi et al.[9] Appropriateness is therefore directly related to the suggested tests in the study intervention. Tests not included in the study order sets are considered inappropriate. The order sets vary according to specific situations. For example, in some cases, an order set for initial diagnosis was used, but in other situations an order set for follow-up was used. In the composite outcome appropriateness, all tests included in the order sets will be considered appropriate for a given indication. Below, we specify exactly which tests will be considered appropriate for each study indication. Tests in red are considered inappropriate when they are absent from the panel for the given indication. Tests for underutilization were identified through the National Institute for Health and Care Excellence (NICE) quality standards.[10] Those tests considered an essential part of any type of laboratory investigation (diagnosis, follow-up, etc.) for one of the study indications were considered inappropriate when not ordered. We identified tests for inappropriate under-utilization for the indications diabetes mellitus, chronic kidney disease, rheumatoid arthritis and thyroid disease.

| Study indication | Test | Code (LOINC) |
|--------------------------------|-----------------------------|--------------|
| Cardiovascular risk assessment | Cholesterol total | 2093-3 |
| Cardiovascular risk assessment | Cholesterol HDL | 2085-9 |
| Cardiovascular risk assessment | Cholesterol total/HDL ratio | 32309-7 |
| Cardiovascular risk assessment | Cholesterol total/HDL ratio | 9830-1 |
| Cardiovascular risk assessment | Triglycerides | 2571-8 |
| Cardiovascular risk assessment | Cholesterol non-HDL | 43396-1 |
| Cardiovascular risk assessment | Cholesterol LDL calc | 13457-7 |
| Cardiovascular risk assessment | Glucose post meal | 16915-1 |
| Cardiovascular risk assessment | Glucose 2h post meal | 6689-4 |
| Cardiovascular risk assessment | Glucose fasting | 1558-6 |
| Cardiovascular risk assessment | Glucose serum | 2345-7 |
| Cardiovascular risk assessment | GGT | 2324-2 |
| Cardiovascular risk assessment | ALT (GPT) | 1742-6 |

Table 2: Appropriate tests for the indication 'cardiovascular risk assessment'.

| Study indication | Test | Code (LOINC) |
|------------------|----------------------------------|--------------|

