| Hypertension | Cholesterol total | 2093-3 |
| Hypertension | Cholesterol HDL | 2085-9 |
| Hypertension | Cholesterol total/HDL ratio | 32309-7 |
| Hypertension | Cholesterol total/HDL ratio | 9830-1 |
| Hypertension | Triglycerides | 2571-8 |
| Hypertension | Cholesterol non-HDL | 43396-1 |
| Hypertension | Cholesterol LDL calc | 13457-7 |
| Hypertension | Glucose post meal | 16915-1 |
| Hypertension | Glucose 2h post meal | 6689-4 |
| Hypertension | Glucose fasting | 1558-6 |
| Hypertension | Glucose serum | 2345-7 |
| Hypertension | GFR MDRD | 33914-3 |
| Hypertension | GFR CKD-EPI | 62238-1 |
| Hypertension | Creatinine | 2160-0 |
| Hypertension | Protein (urine, qualitative) | 50949-7 |
| Hypertension | Blood (urine, qualitative) | 5794-3 |
| Hypertension | TSH | 3016-3 |
| Hypertension | TSH | 11580-8 |
| Hypertension | Potassium (venous) | 39789-3 |
| Hypertension | Potassium | 2823-3 |
| Hypertension | Sodium | 2951-2 |
| Hypertension | Metanephrine | 21019-5 |
| Hypertension | Normetanephrine | 21422-1 |
| Hypertension | Protein/Creatinine ratio (urine) | 16285-9 |

Table 3: Appropriate tests for the indication 'hypertension'.

| Study indication | Test | Code (LOINC) |
|-------------------|-----------------------------|--------------|
| Diabetes mellitus | Cholesterol total | 2093-3 |
| Diabetes mellitus | Cholesterol HDL | 2085-9 |
| Diabetes mellitus | Cholesterol total/HDL ratio | 32309-7 |
| Diabetes mellitus | Cholesterol total/HDL ratio | 9830-1 |
| Diabetes mellitus | Triglycerides | 2571-8 |
| Diabetes mellitus | Cholesterol non-HDL | 43396-1 |
| Diabetes mellitus | Cholesterol LDL calc | 13457-7 |

| | | |
|-------------------|-----------------------------------|---------|
| Diabetes mellitus | Glucose post meal | 16915-1 |
| Diabetes mellitus | Glucose 2h post meal | 6689-4 |
| Diabetes mellitus | Glucose fasting | 1558-6 |
| Diabetes mellitus | Glucose serum | 2345-7 |
| Diabetes mellitus | HbA1C (HPLC) | 17856-6 |
| Diabetes mellitus | HbA1C (IFCC) | 59261-8 |
| Diabetes mellitus | HbA1c | 4548-4 |
| Diabetes mellitus | GFR MDRD | 33914-3 |
| Diabetes mellitus | GFR CKD-EPI | 62238-1 |
| Diabetes mellitus | Creatinine | 2160-0 |
| Diabetes mellitus | Potassium | 2823-3 |
| Diabetes mellitus | Microalbumin (urine) | 14957-5 |
| Diabetes mellitus | Albumine/Creatinine Ratio (urine) | 14959-1 |

Table 4: Appropriate tests for the indication 'diabetes mellitus'.

| Study indication | Test | Code (LOINC) |

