|------------------|----------------------|--------------|
| Fatigue | Glucose post meal | 16915-1 |
| Fatigue | Glucose 2h post meal | 6689-4 |
| Fatigue | Glucose fasting | 1558-6 |
| Fatigue | Glucose serum | 2345-7 |
| Fatigue | ALT (GPT) | 1742-6 |
| Fatigue | GFR MDRD | 33914-3 |
| Fatigue | GFR CKD-EPI | 62238-1 |
| Fatigue | Creatinine | 2160-0 |
| Fatigue | TSH | 3016-3 |
| Fatigue | TSH | 11580-8 |
| Fatigue | Potassium (venous) | 39789-3 |
| Fatigue | Potassium | 2823-3 |
| Fatigue | Sodium | 2951-2 |
| Fatigue | ESR | 4537-7 |
| Fatigue | RBC | 789-8 |
| Fatigue | MCH | 785-6 |
| Fatigue | MCHC | 786-4 |
| Fatigue | MCV | 787-2 |
| Fatigue | Hct | 789-8 |
| Fatigue | Hct | 11273-0 |
| Fatigue | Hct automated | 4544-3 |
| Fatigue | Hb | 718-7 |

| | | |
|---------|---------------------------------------|---------|
| Fatigue | Hb | 785-6 |
| Fatigue | RBC distribution | 788-0 |
| Fatigue | WBC | 6690-2 |
| Fatigue | WBC formula | 49024-3 |
| Fatigue | WBC morphology | 18314-5 |
| Fatigue | WBC leucocytes # | 6690-2 |
| Fatigue | WBC monocytes % | 5905-5 |
| Fatigue | WBC monocytes/leuco | 26485-3 |
| Fatigue | WBC monocytes # | 26484-6 |
| Fatigue | WBC monocytes # automatic | 742-7 |
| Fatigue | WBC lymphocytes % | 26478-8 |
| Fatigue | WBC lymphocytes/leuco | 26578-8 |
| Fatigue | WBC lymphocytes/leuco automatic | 736-9 |
| Fatigue | WBC lymphocytes # | 26474-7 |
| Fatigue | WBC lymphocytes # automatic | 731-0 |
| Fatigue | WBC basophiles # | 704-7 |
| Fatigue | WBC basophiles % | 26444-0 |
| Fatigue | WBC basophiles/leuco | 30180-4 |
| Fatigue | WBC basophiles/100 leuco | 706-2 |
| Fatigue | WBC eosinophiles # | 711-2 |
| Fatigue | WBC eosinophiles % | 26449-9 |
| Fatigue | WBC eosinophiles/leuco | 26450-7 |
| Fatigue | WBC eosinophiles/100 leuco | 713-8 |
| Fatigue | WBC neutrophiles # | 751-8 |
| Fatigue | WBC segm neutrophiles # | 30451-9 |
| Fatigue | WBC segm neutrophiles/leuco | 26505-8 |
| Fatigue | WBC segm neutrophiles/leuco automatic | 32200-8 |
| Fatigue | WBC normoblasts/leuco | 33990-3 |
| Fatigue | WBC normoblasts # | 715-3 |
| Fatigue | WBC myelocytes # | 30446-9 |
| Fatigue | WBC promyelocytes | 26523-1 |
| Fatigue | WBC promyelocytes/leuco | 26524-9 |
| Fatigue | WBC metamyelocytes # | 30433-7 |
| Fatigue | WBC metamyelocytes/leuco | 28541-1 |
| Fatigue | Thrombocytes | 777-3 |
| Fatigue | Leuco + Thrombo morphology | 48705-8 |
| Fatigue | FT4 | 14920-3 |
| Fatigue | Ferritin | 2276-4 |

| | | |

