| Liver disease | CMV IgG IA | 5124-3 |
| Liver disease | CMV IgM Ab IA | 5126-8 |
| Liver disease | Transferrin % | 48495-6 |

Table 9: Appropriate tests for the indication 'liver disease'.

| Study indication | Test | Code (LOINC) |
|------------------|---------------------|--------------|
| Gout | GFR MDRD | 33914-3 |
| Gout | GFR CKD-EPI | 62238-1 |
| Gout | Creatinine | 2160-0 |
| Gout | Urate crystals | 5816-4 |
| Gout | Uric acid (Urate) | 3084-1 |
| Gout | Cholesterol non-HDL | 43396-1 |

Table 10: Appropriate tests for the indication 'gout'.

| Study indication | Test | Code (LOINC) |
|------------------------|-----------------------------|--------------|
| Chronic kidney disease | Cholesterol total | 2093-3 |
| Chronic kidney disease | Cholesterol HDL | 2085-9 |
| Chronic kidney disease | Cholesterol total/HDL ratio | 32309-7 |
| Chronic kidney disease | Cholesterol total/HDL ratio | 9830-1 |
| Chronic kidney disease | Triglycerides | 2571-8 |
| Chronic kidney disease | Cholesterol non-HDL | 43396-1 |
| Chronic kidney disease | Cholesterol LDL calc | 13457-7 |
| Chronic kidney disease | Glucose post meal | 16915-1 |

| | | |
|-------------------------------|-----------------------------------|---------------|
| Chronic kidney disease | Glucose 2h post meal | 6689-4 |
| Chronic kidney disease | Glucose fasting | 1558-6 |
| Chronic kidney disease | Glucose serum | 2345-7 |
| Chronic kidney disease | GFR MDRD | 33914-3 |
| Chronic kidney disease | GFR CKD-EPI | 62238-1 |
| Chronic kidney disease | Creatinine | 2160-0 |
| Chronic kidney disease | Protein/Creatinine ratio (urine) | 16285-9 |
| Chronic kidney disease | Microalbumin (urine) | 14957-5 |
| Chronic kidney disease | Albumine/Creatinine Ratio (urine) | 14959-1 |
| Chronic kidney disease | RBC | 789-8 |
| Chronic kidney disease | MCH | 785-6 |
| Chronic kidney disease | MCHC | 786-4 |
| Chronic kidney disease | MCV | 787-2 |
| Chronic kidney disease | Hct | 789-8 |
| Chronic kidney disease | Hct | 11273-0 |
| Chronic kidney disease | Hct automated | 4544-3 |
| Chronic kidney disease | Hb | 718-7 |
| Chronic kidney disease | Hb | 785-6 |
| Chronic kidney disease | RBC distribution | 788-0 |
| Chronic kidney disease | PTH | 2731-8 |
| Chronic kidney disease | Calcium (Ca) | 2000-8 |
| Chronic kidney disease | 25-OH-Vitamin D | 1990-1 |
| Chronic kidney disease | 25-OH-Vitamin D2 + D3 | 83070-3 |
| Chronic kidney disease | Phosphate | 14879-1 |
| Chronic kidney disease | Bicarbonate | 1963-8 |

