| Acute diarrhea | MCV | 787-2 |
| Acute diarrhea | Hct | 789-8 |
| Acute diarrhea | Hct | 11273-0 |
| Acute diarrhea | Hct automated | 4544-3 |
| Acute diarrhea | Hb | 718-7 |
| Acute diarrhea | Hb | 785-6 |
| Acute diarrhea | RBC distribution | 788-0 |
| Acute diarrhea | Fecal culture | 634-6 |
| Acute diarrhea | Fecal culture | 625-4 |
| Acute diarrhea | EHEC | 21262-1 |
| Acute diarrhea | Giardia lamblia | 31830-3 |
| Acute diarrhea | Microscopy parasites | 10701-1 |
| Acute diarrhea | Rotavirus Ab | 72174-6 |
| Acute diarrhea | Adenovirus Ab | 78529-5 |
| Acute diarrhea | Clostridium difficile | 34713-8 |
| Acute diarrhea | Urea | 3091-6 |

Table 16: Appropriate tests for the indication 'acute diarrhea'.

| Study indication | Test | Code (LOINC) |
|-------------------------|------------------|---------------------|
| Chronic diarrhea | RBC | 789-8 |
| Chronic diarrhea | MCH | 785-6 |
| Chronic diarrhea | MCHC | 786-4 |
| Chronic diarrhea | MCV | 787-2 |
| Chronic diarrhea | Hct | 789-8 |
| Chronic diarrhea | Hct | 11273-0 |
| Chronic diarrhea | Hct automated | 4544-3 |
| Chronic diarrhea | Hb | 718-7 |
| Chronic diarrhea | Hb | 785-6 |
| Chronic diarrhea | RBC distribution | 788-0 |
| Chronic diarrhea | WBC | 6690-2 |

| | | |
|------------------|-----------------------|---------|
| Chronic diarrhea | CRP | 1988-5 |
| Chronic diarrhea | Fecal culture | 634-6 |
| Chronic diarrhea | Giardia lamblia | 31830-3 |
| Chronic diarrhea | Clostridium difficile | 34713-8 |
| Chronic diarrhea | Cryptosporidium | 20781-1 |
| Chronic diarrhea | Calprotectine | 38445-3 |
| Chronic diarrhea | IgA total | 2458-8 |
| Chronic diarrhea | IgA tTGA | 46128-5 |

Table 17: Appropriate tests for the indication 'chronic diarrhea'.

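### The LOINC lists that define the primary outcome accept different codes for the same analyte in different indications, and no rule covers tests whose code cannot be identified

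*SAP*

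**What the plan says.** SAP 10.1.1 adopts a restrictive definition: "Tests not included in the study order sets are considered inappropriate". It presents Tables 2 to 17 as the complete operational definition: "Below, we specify exactly which tests will be considered appropriate for each study indication". Each row of those tables is an indication, a test name and a LOINC code. The same section says that every test in the order sets counts as appropriate for its indication.

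SAP 10.2.1 turns the lists into the outcome. Per patient, it is (a)/(a+b+c), where (a) counts requested appropriate tests, (b) requested inappropriate tests, and (c) tests inappropriately not requested.

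The rows at issue are:
- Potassium: Table 3 has "Hypertension | Potassium (venous) | 39789-3" as well as 2823-3, and Tables 5 and 7 have the same pair. Table 4 has only "Diabetes mellitus | Potassium | 2823-3".
- Fecal culture: Table 16 has 634-6 and also "Acute diarrhea | Fecal culture | 625-4". Table 17 has 634-6 only.
- Lipids in gout: Table 10 has "Gout | Cholesterol non-HDL | 43396-1" and no other lipid row.

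On coding, SAP 6.3.2 maps Medidoc codes to LOINC, but for a small set of tests "the meaning of the original Medidoc code is not retrievable and these tests will not be recoded". It deletes only observations that are not laboratory results, and it does not say how the unrecoded tests are scored. SAP 6.4.2 announces that some tests will be grouped by the original order, because one order can generate several results. It names no code groups.

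**The concern.** These tables are the primary outcome. If the lists are matched by code, as they are written, a result reported under an unlisted code moves from (a) to (b) even when the analyte itself is on that indication's list. The score then depends partly on how a laboratory codes its results and not only on what the physician ordered. It would also conflict with the SAP's own statement that order-set tests count as appropriate.

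The unrecoded Medidoc tests raise a related problem. They can match no list, so the off-list rule taken literally would put them in (b), but the SAP never says that this is intended. Both matters are cheap to settle while the analysis team is blinded. After unblinding, either would be a change to the primary outcome made with knowledge of allocation.

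**Working it through.** The plan states no figure on this point, so the main check is a comparison of the lists. The arithmetic after it is illustrative.

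**1. The lists side by side (SAP 10.1.1)**

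| Analyte | Accepted codes | Tables with all of them | Table lacking some | Missing |
|---|---|---|---|---|
| Potassium | 39789-3, 2823-3 | 3, 5, 7 | 4 (diabetes) | 39789-3 |
| Fecal culture | 634-6, 625-4 | 16 | 17 (chronic diarrhea) | 625-4 |
| Total and HDL cholesterol, listed with non-HDL (43396-1) | 2093-3, 2085-9 | 2, 3, 4, 6, 7, 9, 11 | 10 (gout) | both |

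The discrepancy affects 1 of 4 lists with potassium, 1 of 2 with fecal culture, and 1 of 8 with non-HDL cholesterol. Other analytes with several codes (TSH, glucose, total/HDL ratio, creatinine and GFR, hematocrit, HBsAg) are consistent across their lists. HbA1c appears in one list only.

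**2. Effect on one panel**

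Moving one test from (a) to (b) leaves the denominator unchanged and lowers the ratio by 1/(a+b+c). For a panel of k tests, all appropriate, the ratio becomes (k − 1)/k:
- k = 5 (study tests per panel, protocol 9.1): 4/5 = 0.80
- k = 10 (intermediate value, assumed): 9/10 = 0.90
- k = 14 (about the laboratory averages of 14.2 to 14.61, protocol 4): 13/14 = 0.93

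**3. Which panels are exposed**

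SAP 6.1.1 says that many panels carry more than one indication. If a test counts as appropriate when any ticked study indication lists it, which is how I read SAP 10.2.1, a diabetes panel that also carries hypertension, fatigue or medication follow-up is protected. Only diabetes panels without those three are exposed to the potassium gap.

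**4. Effect on the overall contrast**

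Let m be the share of truly appropriate tests scored inappropriate, equal in both arms. The documents do not give m. The planned 70% and 80% (SAP 2.2.1) become 0.70(1 − m) and 0.80(1 − m), so the difference is 0.10(1 − m):

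| m (assumed) | Control | Intervention | Difference, points |
|---|---|---|---|
| 1% | 69.3% | 79.2% | 9.9 |
| 2% | 68.6% | 78.4% | 9.8 |
| 5% | 66.5% | 76.0% | 9.5 |
| 10% | 63.0% | 72.0% | 9.0 |

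**5. Unidentified tests**

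If such tests make up a share u of the denominator in both arms and are counted in (b), the difference is 0.10(1 − u). At u = 0.5% it is 9.95 points and at u = 5% it is 9.5 points. The share u is also assumed; the SAP says only that the set is small.

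**The case against.** The strongest reply is that some differences may be intended. Acute and chronic diarrhea have clearly different lists, and the gout lipid row may follow the gout order set or be a stray row. Protocol 5.2 refers to Appendix 2 for the order sets, and their contents are not in the text available here. This stands as a reason to check the order sets before adding any code. It is weakest for potassium, which is on the diabetes list already and differs only in code.

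A second reply is that the grouping in SAP 6.4.2 or the mapping in 6.3.2 might merge the codes. Neither says so: 6.4.2 concerns one order that yields several results, and 6.3.2 produces one code system without defining which LOINC codes are synonymous.

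A reader might infer three stronger points, which the documents do not support:
- **That unidentified tests are declared inappropriate.** The SAP is silent. A test of unknown meaning cannot be shown to lie outside the order sets, so this is a missing rule.
- **That shared codes distort the score.** Rows such as "Fatigue | Hct | 789-8" give hematocrit the code also given to RBC, and 785-6 serves both MCH and Hb. Both names always appear in the same list, so the result is accepted either way. Double counting would depend on programming that the SAP does not describe.
- **That the error is biased between arms.** Intervention physicians see preselected tests and controls an empty form (protocol 5.1), so the suspicion is natural. If an assumed 90% of intervention and 40% of control diabetes panels contained one misscored test among 14, the diabetes contrast in that laboratory would shift by (0.9 − 0.4)/14 = 3.6 points against the intervention. Both shares are invented. Nothing shows that any laboratory reports 39789-3 on diabetes panels or that potassium is preselected there. Randomisation was stratified by laboratory (SAP 3.2) and laboratory is a model factor (SAP 10.2.1). These would not remove a scoring error that differed by arm within a laboratory, but no such error is shown.

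**Conclusion.** The inconsistency is real and can be read directly from the tables. Under the rule as written, a potassium result coded 39789-3 on an exposed diabetes panel is scored inappropriate although potassium is on the diabetes list. The fecal culture and gout rows are discrepancies to be explained; they are not established errors.

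The size is unknown, because the documents give neither the code frequencies nor the laboratories concerned. Few rows are involved and co-indications protect some panels, so the effect on the overall primary contrast is probably small: a loss of 0.1 to 0.5 points out of 10 at an assumed 1% to 5% of appropriate tests misscored equally in both arms. The likely direction is dilution. It matters more for the per-indication analyses in SAP 10.2.1, where a single row carries more weight. For unidentified tests the finding is only that the scoring rule is missing. This should be corrected, but it does not by itself threaten the main conclusion.

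**What to change.** Before unblinding:
1. Build one map from every LOINC code to one analyte and apply it identically to all indications.
2. Score at analyte level from a list with one row per analyte and indication. This also removes any question about repeated codes.
3. Check the potassium row in Table 4, the fecal culture row in Table 17 and the lipid row in Table 10 against the order sets. Correct those that are omissions and record a reason for any that are intended.
4. State in SAP 6.3.2 or 10.1.1 whether tests with an unidentifiable Medidoc code are left out of (a+b+c) or counted in (b). Run a sensitivity analysis with the other choice and report how many such tests there are per arm and laboratory.

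The cost is a small amount of blinded data-management work on a lookup table. No new data are needed. SAP 7.2 locks the laboratory database ahead of the final cascade-test collection and SAP 8 unblinds after lock, so the map should be fixed and dated before then.

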10.1.2. Secondary outcome diagnostic error

This outcome is defined in 2 independent ways.

The first is based on the physician's evaluation. During data collection, for every new diagnosis, physicians were asked whether it was related to the laboratory panel and, if so, whether the diagnosis was made correctly and timely. If the physician gives a negative answer to this question, this diagnosis is marked as 'possible diagnostic error'.

The second definition is based on a theoretical evaluation, by two independent researchers, of all occurring combinations of new diagnoses and indications for lab panels. For each combination an algorithm (see figure 2) will be applied in order to become an evaluation of 'no' or 'possible' diagnostic error. In case of dispute, a third independent researcher will be asked to resolve the evaluation. The researchers involved in this theoretical evaluation will be blinded to the allocation of the intervention until all evaluations have been made and validated.

[figure not shown]

Figure 3: Algorithm used for the theoretical evaluation of diagnostic error.

